10.11. Appendix 11: Abbreviations

The following is a list of abbreviations that may be used in the protocol.

Abbreviation	Term
7vPnC	7-valent pneumococcal conjugate vaccine
13vPnC	13-valent pneumococcal conjugate vaccine
20vPnC	20-valent pneumococcal conjugate vaccine
AE	adverse event
ADE	adverse device effect
ADL	activity(ies) of daily living
ALT	alanine aminotransferase
AOM	acute otitis media
AST	aspartate aminotransferase
BCG	bacille Calmette-Guérin
CAP	community-acquired pneumonia
CBER	Center for Biologics Evaluation and Research
CDC	Centers for Disease Control and Prevention
CFR	Code of Federal Regulations
CHMP	Committee for Medicinal Products for Human Use
CI	confidence interval
CIOMS	Council for International Organizations of Medical Sciences
CK	creatin kinase
CLIA	chemiluminescent immunoassay
CONSORT	Consolidated Standards of Reporting Trials
CRF	case report form
CRM ₁₉₇	cross-reactive material 197
CRO	contract research organization
CSAP	clinical specimen assessment plan
CSR	clinical study report
DILI	drug-induced liver injury
DTaP	diphtheria, tetanus, and acellular pertussis vaccine
DU	dispensable unit
EC	ethics committee
ECDC	European Centre for Disease Prevention and Control
EKG	electrocardiogram
eCRF	electronic case report form
EDB	exposure during breastfeeding
e-diary	electronic diary
CCI	
EDB	exposure during breastfeeding
EDP	exposure during pregnancy
ELISA	enzyme-linked immunosorbent assay

PFIZER CONFIDENTIAL

Abbreviation	Term
EMA	European Medicines Agency
EU	European Union
EudraCT	European Clinical Trials Database
FDA	Food and Drug Administration
FHA	filamentous hemagglutinin
GCP	Good Clinical Practice
GGT	gamma-glutamyl transferase
GMC	geometric mean concentration
GMFR	geometric mean fold rise
GMR	geometric mean ratio
GMT	geometric mean titer
HBsAg	hepatitis B surface antigen
HBV	hepatitis B virus
Hib	Haemophilus influenzae type b
HIPAA	Health Insurance Portability and Accountability Act
HIV	human immunodeficiency virus
IB	investigator's brochure
ICD	informed consent document
ICH	International Council for Harmonisation
ID	identification
IgG	immunoglobulin G
IND	investigational new drug application
INR	international normalized ratio
IP manual	investigational product manual
IPD	invasive pneumococcal disease
IPV	inactivated poliovirus vaccine
IRB	institutional review board
IRT	interactive response technology
ISF	investigator site file
IU	international unit(s)
IWR	interactive Web-based response
LFT	liver function test
LLOQ	lower limit of quantitation
MedDRA	Medical Dictionary for Regulatory Activities
MMR	measles, mumps, and rubella vaccine
N/A	not applicable
NA	neutralizing antibody
NDCMC	newly diagnosed chronic medical condition
NI	noninferiority
NIP	national immunization program
OPA	opsonophagocytic activity

PFIZER CONFIDENTIAL

Abbreviation	Term
PCD	primary completion date
PPSV23	23-valent pneumococcal polysaccharide vaccine
PRN	pertactin
PRP	polyribosylribitol phosphate
PT	pertussis toxin
CCI	
SADE	serious adverse device effect
SAE	serious adverse event
SAP	statistical analysis plan
SmPC	summary of product characteristics
SoA	schedule of activities
SOP	standard operating procedure
SRM	study reference manual
SRSD	single reference safety document
SUSAR	suspected unexpected serious adverse reaction
TBili	total bilirubin
ULN	upper limit of normal
US	United States
USADE	unanticipated serious adverse device effect
VT	vaccine-type
WHO	World Health Organization

Appendix 2. Analysis for the Russian Cohort48

1. VERSION HISTORY

Table 1. Summary of Changes

Version/ Date	Associated Protocol Amendment	Rationale	Specific Changes
1 21 Jun 2021	Amendment 2 18 June 2021	N/A	N/A

2. INTRODUCTION

This SAP provides the detailed methodology for summary and statistical analyses of the data collected in Study B7471012. This document may modify the plans outlined in the protocol; however, any major modifications of the primary endpoint definition or its analysis will also be reflected in a protocol amendment. The impacts of COVID-19 will be assessed prior to the analysis of safety and immunogenicity results from the primary study population, and the SAP will be amended accordingly to account for these impacts, if needed.

2.1. Study Objectives, Endpoints, and Estimands

The estimands corresponding to each primary, secondary, CCI objective are described in Table 2. The objectives, estimands, and endpoints table for the Russian cohort can be found in Appendix 2. The estimands to evaluate the immunogenicity objectives for NI are based on evaluable populations (see Section 4 for definition). These estimands estimate vaccine effect in the hypothetical setting where participants follow the study schedules and protocol requirements as directed. The estimand addresses the objective of estimating the maximum potential difference between 2 groups (20vPnC and 13vPnC), since the impact of noncompliance is likely to diminish the observed difference between the 2 groups. Missing serology results will not be imputed. Immunogenicity results that are below the LLOQ, denoted as BLQ, will be set to $0.5 \times \text{LLOQ}$ in the analysis.

In the primary safety objective evaluations, missing e-diary data will not be imputed. Missing AE dates will be imputed according to Pfizer safety rules (Section 5.3). No other missing information will be imputed in the safety analysis.

Table 2. List of Primary, Secondary, CCI Objectives, Endpoints, and Estimands for Primary Study Population

Primary Safety Objective	Estimands	Primary Safety Endpoints
To describe the safety profile of 20vPnC	In participants receiving at least 1 dose of investigational product and having safety data reported after any vaccination in each vaccine group: 
 • The percentage of participants reporting prompted local reactions within 7 days after each dose • The percentage of participants reporting prompted systemic events within 7 days after each dose • The percentage of participants reporting AEs from Dose 1 to 1 month after Dose 2 and from Dose 3 to 1 month after Dose 3 • The percentage of participants reporting SAEs through 1 month after Dose 3 • The percentage of participants reporting NDCMCs through 1 month after Dose 3 	
 • Prompted local reactions (redness, swelling, and pain at the injection site) • Prompted systemic events (fever, decreased appetite, drowsiness/increased sleep, and irritability) • AEs • SAEs • NDCMCs
Primary Pneumococcal Immunogenicity Objectives	Estimands	Primary Pneumococcal Immunogenicity Endpoints
To demonstrate that the percentages of participants with predefined serotype-specific IgG concentrations for the 13 serotypes in the 20vPnC group are noninferior to those of the corresponding serotypes in the 13vPnC group at 1 month after Dose 2	In evaluable participants defined in Section 4 at 1 month after Dose 2: 
 • For each of the 13 matched serotypes: difference in the percentages of participants with predefined IgG concentrations between the 20vPnC group and the 13vPnC group 	
 • Pneumococcal IgG concentrations
To demonstrate that the percentages of participants with predefined serotype-specific IgG concentrations for the 7 additional serotypes in the 20vPnC group are noninferior to the lowest among the 13 serotypes in the 13vPnC group at 1 month after Dose 2	In evaluable participants at 1 month after Dose 2: 
 • For each of the 7 additional serotypes in 20vPnC: difference in the percentages of participants with predefined IgG concentrations between the 20vPnC group and the lowest percentage of participants with predefined IgG concentrations among the 13 serotypes from the 13vPnC group 	
 • Pneumococcal IgG concentrations

Table 2. List of Primary, Secondary, CCI Objectives, Endpoints, and Estimands for Primary Study Population

To demonstrate that the serotype-specific IgG GMCs for the 13 serotypes in the 20vPnC group are noninferior to those for the corresponding serotypes in the 13vPnC group at 1 month after Dose 2	In evaluable participants at 1 month after Dose 2: 
 For each of the 13 matched serotypes: GMRs of IgG concentrations from the 20vPnC group to the 13vPnC group 	
 Pneumococcal IgG concentrations
To demonstrate that the serotype-specific IgG GMCs for the 7 additional serotypes in the 20vPnC group are noninferior to the lowest among the 13 serotypes in the 13vPnC group at 1 month after Dose 2	In evaluable participants at 1 month after Dose 2: 
 For each of the 7 additional serotypes in 20vPnC: GMRs of IgG concentrations from the 20vPnC group to that from the serotype with the lowest IgG GMC among the 13 serotypes from the 13vPnC group 	
 Pneumococcal IgG concentrations
To demonstrate that the serotype-specific IgG GMCs for the 13 serotypes in the 20vPnC group are noninferior to those for the corresponding serotypes in the 13vPnC group at 1 month after Dose 3	In evaluable participants at 1 month after Dose 3: 
 For each of the 13 matched serotypes: GMRs of IgG concentrations from the 20vPnC group to the 13vPnC group 	
 Pneumococcal IgG concentrations
To demonstrate that the serotype-specific IgG GMCs for the 7 additional serotypes in the 20vPnC group are noninferior to the lowest among the 13 serotypes in the 13vPnC group at 1 month after Dose 3	In evaluable participants at 1 month after Dose 3: 
 For each of the 7 additional serotypes in 20vPnC: GMRs of IgG concentrations from the 20vPnC group to that from the serotype with the lowest IgG GMC among the 13 serotypes from the 13vPnC group 	
 Pneumococcal IgG concentrations
Primary Concomitant Immunogenicity Objective	Estimands	Primary Concomitant Immunogenicity Endpoints
To demonstrate that the immune responses induced by concomitant vaccine antigens given with 20vPnC are noninferior to immune responses induced by concomitant vaccine antigens given with 13vPnC at 1 month after Dose 3	In evaluable participants who receive the appropriate concomitant vaccines: 
 Differences in percentages of participants with prespecified antibody levels to diphtheria toxoid, tetanus toxoid, pertussis antigens (PT, FHA, PRN), HBsAg, poliovirus strains, and Hib 1 month after Dose 3 between the 20vPnC and the 13vPnC groups GMRs of antibody levels to MMR and varicella antigens from the 20vPnC group to the 13vPnC group 1 month after Dose 3 	
 Antibody levels to diphtheria toxoid, tetanus toxoid, and pertussis antigens (PT, FHA, PRN) Antibody levels to HBsAg Antibody levels to poliovirus strains (types 1, 2, and 3) Antibody levels to Hib Antibody levels to MMR and varicella viruses

Table 2. List of Primary, Secondary, CCI Objectives, Endpoints, and Estimands for Primary Study Population

Secondary Pneumococcal Immunogenicity Objective	Estimands	Secondary Pneumococcal Immunogenicity Endpoints
To further describe the immune responses induced by 20vPnC	In evaluable participants: 
 • For each of the 13 matched serotypes: difference in the percentages of participants with predefined IgG concentrations between the 20vPnC group and the 13vPnC group at 1 month after Dose 3 • For each of the 7 additional serotypes in 20vPnC: difference in the percentages of participants with predefined IgG concentrations between the 20vPnC group and the lowest percentage of participants with predefined IgG concentrations among the 13 serotypes from the 13vPnC group at 1 month after Dose 3 • For each of the 20 serotypes in 20vPnC: OPA GMTs 1 month after Dose 2 and 1 month after Dose 3 in each vaccine group • For each of the 20 serotypes in 20vPnC: GMFRs in IgG concentrations from before Dose 3 to 1 month after Dose 3 in each vaccine group 	
 • Pneumococcal IgG concentrations • Pneumococcal OPA titers
Secondary Concomitant Immunogenicity Objective	Estimand	Secondary Concomitant Immunogenicity Endpoints
To further describe the immune responses induced by specific concomitant vaccine antigens given with 20vPnC or 13vPnC	In evaluable participants who receive appropriate concomitant vaccines: 
 • Differences in percentages of participants with prespecified antibody levels to diphtheria toxoid, tetanus toxoid, pertussis antigens (PT, FHA, PRN), poliovirus strains, and Hib 1 month after Dose 2 between the 20vPnC and the 13vPnC groups 	
 • Antibody levels to diphtheria toxoid, tetanus toxoid, and pertussis antigens (PT, FHA, PRN) • Antibody levels to poliovirus strains (types 1, 2, and 3) • Antibody levels to Hib

Table 2. List of Primary, Secondary, CCI [REDACTED] Objectives, Endpoints, and Estimands for Primary Study Population

The table content is almost entirely obscured by a large black redaction box. The only visible text within this box is the acronym "CCI" in large, bold, red font at the top left.

Table 2. List of Primary, Secondary, CCI Objectives, Endpoints, and Estimands for Primary Study Population

		
--	------------------------------------------------------------------------------------	--

2.2. Study Design

This Phase 3, multicenter, randomized, double-blind study will be conducted at investigator sites in the European Union and Australia (primary study population), with an additional cohort from Russia (Russian cohort).

The primary study population will consist of 1200 infants >36 weeks of gestation and ≥ 42 to ≤ 112 days of age at the time of consent by a parent(s)/legal guardian(s). Participants will be randomized in a 1:1 ratio to receive either 20vPnC or 13vPnC (control vaccine) by site-based randomization. Participants will receive the same vaccine (either 20vPnC or 13vPnC) for all 3 doses at roughly 2, 4, and 11 to 12 months of age (Doses 1, 2, and 3, respectively). A specific vaccine containing DTaP, HBV, IPV, and Hib antigens will be administered concomitantly with all doses of 20vPnC or 13vPnC. Vaccines containing MMR and varicella antigens are also to be administered with Dose 3. These vaccines are intended to be given to all participants. However, in case of circumstances due to local practice/recommendations, some sites may not administer them to their participants at Dose 3, in which case MMR and varicella vaccines will be considered nonstudy vaccines.

Blood will be drawn from all participants for immunogenicity assessments 1 month after Dose 2, immediately prior to receipt of Dose 3, and 1 month after Dose 3. A subset of participants, based on consent to additional optional blood draws offered at certain sites, will have blood collected for immunogenicity assessments prior to Dose 1 and prior to Dose 2. Participants will be observed for 30 minutes after each vaccination and any reactions occurring during that time will be recorded as AEs. Prompted local reactions (redness, swelling, and pain at the 20vPnC or 13vPnC injection site) and systemic events (fever, decreased appetite, drowsiness/increased sleep, and irritability), and use of antipyretic/pain medications occurring within 7 days after each vaccination will be collected via a provided e-diary (or e-diary application). AEs, including nonserious AEs, will be collected from the signing of informed consent to 1 month after Dose 2 and from Dose 3 to 1 month after Dose 3. SAEs and NDCMCs will be collected for the entire duration of the study.

Approximately 60 additional participants will be enrolled in the Russian cohort. Due to timing of the submission of the clinical trial application, the Russian cohort will begin enrollment after the completion of enrollment of the primary study population. The schedule of visits for Russian participants will have a narrower window for age at enrollment and follow a somewhat modified visit window, in line with the Russian NIP (these are described in Section 10.10.4 of the protocol appendix). Russian participants will not receive MMR and varicella vaccinations as part of the study. They will receive MMR and varicella as per local requirements/NIP. Russian participants will not be requested to take part in the blood draws prior to Dose 1 and prior to Dose 2 but will participate in the required blood draws 1 month after Dose 2, before Dose 3, and 1 month after Dose 3.

3. ENDPOINTS AND BASELINE VARIABLES: DEFINITIONS AND CONVENTIONS

3.1. Primary Endpoints

3.1.1. Primary Safety Endpoints

- Prompted local reactions (redness, swelling, and pain at the injection site) within 7 days after each dose
- Prompted systemic events (fever, decreased appetite, drowsiness/increased sleep, and irritability) within 7 days after each dose
- AEs from Dose 1 to 1 month after Dose 2 and from Dose 3 to 1 month after Dose 3
- SAEs during the study (from Dose 1 to 1 month after Dose 3)
- NDCMCs during the study (from Dose 1 to 1 month after Dose 3)

3.1.1.1. Local Reactions

The local reactions assessed and reported in the e-diary are redness, swelling, and pain at the 20vPnC or 13vPnC injection site, from Day 1 through Day 7 after each dose, where Day 1 is the day of each dose. This section describes derivations with details for the assessment of local reactions: presence, severity level, duration, and onset day.

Severity and Maximum Severity

Redness and swelling will be measured and recorded in measuring device (caliper) units (range: 1 to 14 and >14) and then categorized during analysis as mild, moderate, or severe based on the grading scale in [Table 3](#). Grade 4 will not be collected in the e-diary but will be collected as an AE on the CRF. Measuring device units can be converted to centimeters according to the following scale: 1 measuring device unit = 0.5 cm. Pain at the vaccine injection site will be assessed by the participant's parent(s)/legal guardian(s) as mild, moderate, or severe according to the grading scale in [Table 3](#).

Table 3. Grading Scales for Local Reactions

Local Reaction	Grade 1 Mild	Grade 2 Moderate	Grade 3 ^a Severe	Grade 4 ^b
Redness	1 to 4 caliper units (or measuring device units) = >0 to 2.0 cm	5 to 14 caliper units (or measuring device units) = >2.0 to 7.0 cm	>14 caliper units (or measuring device units) = >7.0 cm	Necrosis or exfoliative dermatitis
Swelling	1 to 4 caliper units (or measuring device units) = >0 to 2.0 cm	5 to 14 caliper units (or measuring device units) = >2.0 to 7.0 cm	>14 caliper units (or measuring device units) = >7.0 cm	Necrosis
Pain at injection site	Hurts if gently touched (eg, whimpers, winces, protests, or withdraws)	Hurts if gently touched with crying	Causes limitation of limb movement	Emergency room visit or hospitalization for severe pain (tenderness) at injection site

Abbreviation: CRF = case report form; e-diary = electronic diary.

Note: If the size of the redness and/or swelling falls between 2 measuring device units, the higher measuring device unit number will be recorded in the e-diary.

- a. The parent(s)/legal guardian(s) of the participants experiencing local reactions >14 caliper units (>7.0 cm) are to be contacted by the study site. An unscheduled visit may be required.
- b. Grade 4 assessment should be made by the investigator. Grade 4 will not be collected in the e-diary but will be collected as an AE on the CRF.

For each local reaction after each dose, the maximum severity grade will be derived for the e-diary collection period (Day 1 through Day 7, where Day 1 is the day of each dose) as follows:

maximum severity grade = highest grade (maximum severity) within 7 days after vaccination (Day 1 through Day 7) among severity grades reported for that local reaction in the e-diary.

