Pain at injection site (tenderness)	Hurts if gently touched (eg, whimpers, winces, protests, or withdraws)	Hurts if gently touched with crying	Causes limitation of limb movement	Emergency room visit or hospitalization for severe pain (tenderness) at injection site

Abbreviations: CRF = case report form; e-diary = electronic diary.

- Parent(s)/legal guardian(s) of the participants experiencing local reactions >14 caliper units (>7.0 cm) are to be contacted by the study site. An unscheduled visit may be required.
- Grade 4 assessment should be made by the investigator. Grade 4 will not be collected in the e-diary but will be collected as an AE on the CRF (see [Section 10.3.4](#)).

Note: If the size of the redness and/or swelling falls between 2 measuring device units, the higher measuring device unit number will be recorded in the e-diary.

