9.4.2. Safety Analyses

All safety analyses will be performed on the safety population.

Endpoint	Statistical Analysis Methods
Primary safety	
• Descriptive statistics will be provided for each reactogenicity endpoint for each dose and vaccine group. Local reactions and systemic events from Day 1 through Day 7 after each vaccination will be presented by severity cumulatively across severity levels. Descriptive summary statistics will include counts and percentages of participants with the indicated endpoint and the associated 2-sided Clopper-Pearson 95% CIs. Between-group differences (20vPnC – 13vPnC) in these percentages and their 2-sided 95% CIs will also be provided. The Miettinen and Nurminen method will be used to derive the 95% CI for the difference in percentages between vaccine groups.• AEs will be categorized according to Medical Dictionary for Regulatory Activities (MedDRA) terms. A 3-tier approach will be used to summarize AEs. Under this approach AEs are classified into 1 of 3-tiers: (1) Tier 1 events are prespecified events of clinical importance and are identified in a list in the product’s safety review plan; (2) Tier 2 events are those that are not Tier 1 but are considered “relatively common”; a MedDRA preferred term is defined as a Tier 2 event if there are at least 1% of participants in at least 1 vaccine group reporting the event; and (3) Tier 3 events are those that are neither Tier 1 nor Tier 2 events. For both Tier 1 and Tier 2 events, the 2-sided 95% CIs for the difference in percentage of participants reporting the events between the 20vPnC and 13vPnC groups will be calculated using the Miettinen and

Endpoint	Statistical Analysis Methods

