
The investigator will make an assessment of intensity for each AE and SAE reported during the study and assign it to 1 of the following categories:
 
 • Mild: An event that is easily tolerated by the participant, causing minimal discomfort and not interfering with everyday activities. • Moderate: An event that causes sufficient discomfort and interferes with normal everyday activities. • Severe: An event that prevents normal everyday activities. An AE that is assessed as severe should not be confused with an SAE. Severe is a category utilized for rating the intensity of an event; and both AEs and SAEs can be assessed as severe. 
An event is defined as “serious” when it meets at least 1 of the predefined outcomes as described in the definition of an SAE, NOT when it is rated as severe.
		
GRADE	If required on the AE page of the CRF, the investigator will use the adjectives MILD, MODERATE, or SEVERE to describe the maximum intensity of the AE. For purposes of consistency, these intensity grades are defined as follows:	
1	MILD	Does not interfere with participant's usual function.
2	MODERATE	Interferes to some extent with participant's usual function.
3	SEVERE	Interferes significantly with participant's usual function.

Assessment of Causality

 • The investigator is obligated to assess the relationship between study intervention and each occurrence of each AE/SAE. • A “reasonable possibility” of a relationship conveys that there are facts, evidence, and/or arguments to suggest a causal relationship, rather than a relationship cannot be ruled out. • The investigator will use clinical judgment to determine the relationship. • Alternative causes, such as underlying disease(s), concomitant therapy, and other risk factors, as well as the temporal relationship of the event to study intervention administration will be considered and investigated.

Assessment of Causality

- The investigator will also consult the IB and/or product information, for marketed products, in his/her assessment.
- For each AE/SAE, the investigator **must** document in the medical notes that he/she has reviewed the AE/SAE and has provided an assessment of causality.

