3.1.1.4. Adverse Events

AEs will be categorized according to MedDRA terms. AEs will be assessed from the time of informed consent through 1 month after Dose 2 and from Dose 3 through 1 month after Dose 3.

AEs will be summarized by SOC and preferred term on a participant level.

This primary endpoint will be supported by summaries and listings of related AEs, severe AEs, and immediate AEs (within the first 30 minutes after each dose).

AE reporting will be based on the specific reporting period. Standard algorithms for handling missing AE dates will be applied as described in the Pfizer Vaccines data standards rules as described in [Section 5.3](#).

A 3-tier approach will be used to summarize AEs from Dose 1 through 1 month after Dose 2 and, separately, from Dose 3 through 1 month after Dose 3. Under this approach, AEs are classified into 1 of 3 tiers. Different analyses will be performed for different tiers (see [Section 6.1.1.3.1](#)).

- Tier 1 events: These are prespecified events of clinical importance and are identified in a list in the product’s safety review plan. No Tier 1 events have been identified to date for 20vPnC.

- Tier 2 events: These are events that are not Tier 1 but are “relatively common.” A MedDRA preferred term is defined as a Tier 2 event if there are at least 1% of participants with the AE term in at least 1 vaccine group.
- Tier 3 events: These are events that are neither Tier 1 nor Tier 2.

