6.1.1.1.1. Main Analysis

- Estimand: The percentage of participants reporting prompted local reactions (redness, swelling, and pain at the injection site) within 7 days after each dose (Section 2.1).
- Analysis set: Safety population (Section 4).
- Analysis time point: Within 7 days after each dose.
- Analysis methodology: For percentages of each vaccine group, the 2-sided Clopper-Pearson CIs will be calculated. The between-group difference (20vPnC – 13vPnC) and the corresponding 2-sided 95% CI will be calculated using the Miettinen and Nurminen method (Section 5.2.1).
- Intercurrent events and missing data: Missing values will not be imputed. CCI
CCI
- Reporting results: Count and percentage of participants with the indicated endpoint and the associated 2-sided 95% CI for each and any local reaction after each dose in each vaccine group will be presented by maximum severity across severity levels. Between-group differences (20vPnC – 13vPnC) in these percentages and their 2-sided 95% CIs will also be provided.

CCI

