6.1.1.4. Serious Adverse Events and Newly Diagnosed Chronic Medical Conditions

6.1.1.4.1. Main Analyses

- Estimands:
 - The percentage of participants reporting SAEs from Dose 1 to 1 month after Dose 3 ([Section 2.1](#)).
 - The percentage of participants reporting NDCMCs from Dose 1 to 1 month after Dose 3 ([Section 2.1](#)).
- Analysis set: Safety population ([Section 4](#)).
- Analysis time point: Dose 1 to 1 month after Dose 3.
- Analysis methodology: For percentages, the 2-sided Clopper-Pearson CIs will be calculated for each vaccine group ([Section 5.2.1](#)).
- Intercurrent events and missing data: No missing values will be imputed except for partial SAE/NDCMC start dates ([Section 5.3](#)).
- Reporting results: The numerator (n) and the denominator (N) used in the percentage calculation, the percentage (%), and the corresponding 2-sided Clopper-Pearson 95% CI for participants reporting any SAEs/NDCMCs, by each SOC, and each preferred term within SOCs will be presented by vaccine group. SAEs and NDCMCs will be presented separately.

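### Do the by-dose reactogenicity tables hide Grade 4 prompted reactions, because maximum severity is taken from the e-diary alone?

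*SAP*

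**What the plan says.** SAP 3.1.1.1 defines the maximum severity grade of a local reaction over Days 1 to 7 as the highest grade "among severity grades reported for that local reaction in the e-diary". SAP 3.1.1.2 says that the systemic-event derivations follow the local-reaction ones in a similar way. SAP Tables 3 and 4 nevertheless define a fourth grade. For redness this is necrosis or exfoliative dermatitis, and for swelling it is necrosis. For pain, decreased appetite, drowsiness and irritability it is an emergency room visit or hospitalization for the severe symptom.

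Both documents say where the fourth grade goes. In the SAP: "Grade 4 will not be collected in the e-diary but will be collected as an AE on the CRF". In the protocol, under Table 1 in 8.2.2.1: "Grade 4 assessment should be made by the investigator. Grade 4 will not be collected in the e-diary", followed by the same routing to the CRF. The notes to SAP Table 4 and protocol Table 2 repeat this for systemic symptoms.

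On output, SAP 6.1.1.1.1 says that local reactions after each dose in each vaccine group "will be presented by maximum severity across severity levels", and 6.1.1.2.1 uses the same form for systemic events. Protocol 9.4.2 plans the same display: "Local reactions and systemic events from Day 1 through Day 7 after each vaccination will be presented by severity cumulatively across severity levels". SAP section 4 states that these summaries rest on e-diary data, from participants in the safety population with any such data.

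**The concern.** Prompted reactions within 7 days of each dose are a primary safety endpoint. Read together, the derivation and the routing rule mean that the most severe grade the plan defines can never appear in the tables that present the endpoint by severity. The missing Grade 4 row cannot be read as zero events.

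The AE outputs do not obviously fill that space:

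- AE tables are organized by system organ class and preferred term, and Doses 1 and 2 are pooled through 1 month after Dose 2 (SAP 6.1.1.3.1).
- SAEs are pooled over the whole study ("Analysis time point: Dose 1 to 1 month after Dose 3").
- The AE intensity scale in protocol 10.3.4 has three levels: "If required on the AE page of the CRF, the investigator will use the adjectives MILD, MODERATE, or SEVERE to describe the maximum intensity". A Grade 4 prompted reaction therefore carries the same label as any other severe AE.
- An emergency room visit alone can meet Grade 4 without meeting a seriousness criterion, so the SAE tables need not hold every Grade 4 event.

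There is also a route to a grade that is too low. Grades 1 to 3 of redness and swelling depend on size, while Grade 4 depends on tissue damage. Necrosis inside a small measured area would be tabulated as mild or moderate. At stake is whether a reader of the reactogenicity tables could overlook a rare but important local or systemic event.

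**Working it through.** **The plan's own figure.** Protocol Table 7 gives the only stated number for the safety endpoint: the chance of at least one event in 600 infants, 1 − (1 − p)^600. At p = 0.4% this is 1 − 0.996^600 = 0.9097, against the stated 91.0%. The other four rows reproduce as well (45.1%, 69.9%, 83.5% and 95.1%). The concern does not dispute this table. It only supplies the planned 600 per group. The e-diary denominators will be somewhat smaller.

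**Scale of one event.** The documents give no Grade 4 rate, so none is assumed.

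| Quantity | Estimate | 95% interval | Method |
|---|---|---|---|
| One infant in a group, 1/600 | 0.17% | 0.004% to 0.93% | Clopper-Pearson |
| No infant in a group, 0/600 | 0% | upper limit 0.61% | Clopper-Pearson |
| 1/600 minus 0/600 | 0.17 points | −0.47 to 0.94 points | Miettinen-Nurminen |

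These are the methods the SAP names for these tables. The intervals would apply to any single event in any safety table, so they show scale and do not measure harm from this rule.

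**What the tables would show, by reaction.**

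- *Pain, decreased appetite, drowsiness, irritability.* Grade 4 is a visit or admission for a symptom that is already severe. A consistent diary entry is therefore Grade 3. The infant is counted in the highest diary category and only the Grade 4 label is lost. A lower grade, or none, appears only if the diary entry is missing or lower.
- *Redness and swelling.* One caliper unit is 0.5 cm. Necrosis within 1 to 4 units (4 × 0.5 = 2.0 cm) would be shown as mild, and within 5 to 14 units (14 × 0.5 = 7.0 cm) as moderate. This is the only way a complete and consistent diary gives too low a grade.
- *Fever.* It has no Grade 4. It is reported by temperature range up to above 40.0°C and is unaffected.

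The percentage of infants with any reaction changes only if the diary shows no reaction at all in an infant classified as Grade 4, by 1/600 = 0.17 points per infant.

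**Where the events are reported instead.**

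| Output | Shows | Does not state |
|---|---|---|
| AE tables (SAP 6.1.1.3.1) | Preferred term by group, with Dose 3 separate from Doses 1 and 2 | Prompted-reaction grade |
| Supporting AE outputs (SAP 3.1.1.4): "This primary endpoint will be supported by summaries and listings of related AEs, severe AEs, and immediate AEs" | Severe events, summarized and listed | Grade 4 as such |
| SAE tables (SAP 6.1.1.4.1) | Hospitalized or otherwise serious cases, Doses 1 to 3 pooled | Dose, prompted-reaction grade |

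Protocol 10.3.4 asks the investigator to record a diagnosis as the AE wherever possible. Necrosis, the one event a full diary could understate, would then ordinarily appear under its own preferred term and not be buried in a redness row.

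**Whether the three-level table is an accident.** Protocol 8.2.2.1 and SAP 3.1.1.1 both say that redness and swelling are sorted at analysis into mild, moderate or severe. Pain and the systemic symptoms are graded by the parent on the same three levels. In the grading tables only Grades 1 to 3 carry a severity word. The severity levels in the output sections are therefore most naturally these three, and the SAP does not depart from the protocol.

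**The case for a change.** The strongest case for acting is that the plan treats Grade 4 as important enough to define for six reactions and to require immediate notification of the sponsor, yet names no place where a reader will find it. An AE record of a prompted reaction is not in itself a Grade 4 marker: prompted reactions that lead to withdrawal are also entered as AEs, as are reactions seen in the 30-minute observation. A footnote and a listing would cost little.

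Part of this stands. The readable text names no output that identifies Grade 4 by reaction, dose and group. Three things keep it from requiring a change.

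- Parts of SAP 3.1.1 and 6.1.1 are redacted, including text in the two output sections, and a Grade 4 or supplementary display could sit there. The absence cannot be established.
- A footnote marking the tables as e-diary Grades 1 to 3 would repeat what the SAP already says under its grading tables.
- The stronger remedy, letting the investigator's Grade 4 override the diary grade, is debatable. It would put parent-graded and investigator-graded records in one row. It also depends on a Grade 4 flag that the documents do not confirm is in the database, since the AE intensity scale has three levels. Recovering the flag from source records would be extra data capture.

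**Conclusion.** No change follows. The reading of the derivation is correct: the by-dose tables are e-diary tables and stop at severe. That is a stated and consistent design choice, and Grade 4 events are collected and reported as AEs and, where criteria are met, as SAEs. What is missing from the readable text is reporting detail that whoever prepares the table shells can supply: a note that the tables show e-diary grades, and a listing of Grade 4 prompted reactions if the CRF holds the classification.

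The size is small: 0.17 percentage points per infant at 600 per group, and in most cases a lost label with no miscounted infant. This rests on the planned group size and on diary entries that agree with the investigator's account. No Grade 4 rate is assumed. No noninferiority test or immunogenicity estimate is affected, and no safety conclusion is shown to be wrong.
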